9.5 Safety and Tolerability Assessments

9.5.1 Adverse events

Where changes in severity are recorded in the Case Report Form (CRF), each separate severity of the AE will be reported in the listings, only the most severe will be used in the summary tables. A pre-existing condition is defined as an AE that starts before the subject has provided written informed consent and is ongoing at consent. A non-treatment emergent AE is defined as an AE which starts after informed consent but prior to dosing. A treatment-emergent AE is defined as an AE which occurs postdose or which is present prior to dosing and becomes more severe postdose.

All AEs will be listed. Treatment-emergent AEs will be summarized by part, treatment, severity and relationship to the study drug. The frequency (the number of AEs, the number of subjects experiencing an AE and the percentage of subjects experiencing an AE) of treatment-emergent AEs will be summarized by part, treatment, Medical Dictionary for Regulatory Activities (MedDRA) version 21.1 system organ class and preferred term. The summary and frequency AE tables will be presented for all causalities and those considered related to the study drug. Any serious AEs will be listed. For Part B only, AEs by day of onset will be presented.

9.5.2 Concomitant medication

Concomitant medication will be coded using the World Health Organization drug dictionary (Version September 2018). Concomitant medication will be listed.

9.5.3 Clinical laboratory parameters

All clinical chemistry and hematology data will be summarized by part, parameter and treatment, and listed. Where postdose data is available, changes from baseline, where baseline is defined as Day 1 predose will also be presented. Urinalysis data will be listed. Additionally, clinical chemistry, hematology and urinalysis data outside the reference ranges will be listed and flagged on individual subject data listings.

9.5.4 Vital signs

Vital signs data will be summarized by part, treatment and timepoint, together with changes from baseline, where baseline is defined as the Day 1 predose assessment. Figures of mean vital signs and mean changes from baseline profiles will be presented by part and treatment.

Values for individual subjects will be listed.

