Pregnancy test				X	X	Serum test at screening and admission; urine test at all other time points. Women with confirmed nonchildbearing potential status can be exempted from further pregnancy tests during the study after screening.
Neurological exam (hours) ^a	48					The 8-hour time point is optional.
Clinical laboratory tests			X	X	X	See Appendix 2 , Clinical Laboratory Tests, for details. PI must review the Day -2 laboratory result before dosing on Day 1
ABPM	X					The ABPM on Day -1 is a 24-hour collection for baseline measurement. On dosing days, the ABPM recording will be initiated approximately 2 hours prior to dosing for measurement of predose baseline.
Administration of itraconazole	X	X				Itraconazole 200 mg will be administered twice daily on Day 8 (dose separated by 12 hours) and once daily on Days 9 through 17. Itraconazole should be administered at approximately the same time every morning. For the outpatient dosing days, subjects will record the actual time of dose administration on a diary card. On Day 14, itraconazole should be administered 1 hour before LY3154885 administration (see Section 5.1.2).
Vital signs (BP, PR [supine], temperature) (hours) ^a	48, 60	72	96	X	X	Time points may be added for each study period, if clinically indicated. On Day 1, temperature will be measured at predose only.
12-lead ECG			X	X	X	Single safety ECGs.
PGx Sample						Single sample for pharmacogenetic analysis.
LY3154885 PK sampling (hours) ^a	48, 60	72	96			Sampling times are relative to the time of LY3154885 administration (0 hour).

Note: Site should schedule activities as appropriate. In cases where several study procedures are scheduled at the same time, follow this order of priority for procedures: ECG, vital signs, PK samples, and clinical laboratory tests.

Abbreviations: ABPM = ambulatory blood pressure monitoring; AE = adverse event; BP = blood pressure; CRU = clinical research unit; CYP = cytochrome P450; ECG = electrocardiogram; ED = early discontinuation; MA = medical assessment; PE = physical examination; PI = principal investigator; PK = pharmacokinetic; PR = pulse rate.

a Predose time points refer to dosing before itraconazole and LY3154885. All postdose time points are relative to the LY3154885 dose.

Study Schedule Protocol J1Z-MC-HUAA (Part C: Multiple-Ascending Dose – Single Period)

	Screening	Days										ED	Follow-up	Comments
Procedure	-28 to -3	-2	-1	1	2	3-6	7	8-13	14	15		Approx 7 days after discharge		

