5.1.2. Part B (CYP3A4 Inhibition)

Part B will consist of approximately 12 subjects [9 LY3154885; 3 placebo] and will assess the effect of itraconazole, a CYP3A4 inhibitor, on the safety, tolerability, and PK of LY3154885. The LY3154885 dose to be studied in Part B will be determined based on safety, tolerability, and PK data from Part A and will be administered as a capsule formulation. See Section 5.5 for further LY3154885 dose justification.

As detailed in the Schedule of Activities (Section 2), subjects will be admitted to the CRU in the afternoon of Day -2 for set up of baseline ABPM (see Section 9.4.4) and will undergo an overnight fast (see Section 6.3.1) before receiving a single oral dose of LY3154885 or placebo on Day 1. Subjects may be discharged from the CRU on Day 3 and will be re-admitted on Day 7. There will be a 7-day washout period followed by 10 days of dosing with 200 mg itraconazole (twice daily on Day 8 [dose separated by 12 hours], then once daily on Days 9 through 17). See Section 6.3.1 for the fasting requirements for the itraconazole dosing. Subjects will be discharged from the CRU on Day 9 after receiving their dose of itraconazole and will be self-dosing on an outpatient basis from Days 10 through 12. Subjects will be asked to complete a diary card to document the actual date and time of dose administration.

Subjects will be re-admitted to the CRU in the evening of Day 12 and will undergo an overnight fast (see Section 6.3.1) before receiving a single oral dose of LY3154885 or placebo on Day 14, approximately 1 hour after the dose of itraconazole. Blood sampling for PK purposes (LY3154885 and itraconazole) will occur according to the Schedule of Activities in Section 2. Subjects will remain in the CRU until discharge on the morning of Day 18, approximately 24 hours after the final dose of itraconazole.

Figure HUAA.5.2 illustrates the study design for Part B.

[figure not shown]

Figure HUAA.5.2. Illustration of study design for Part B.

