5.1.4. Optional Part D (Pharmacokinetics of Capsule and Tablet Formulations and Food Effect)

The decision to conduct Part D will be made after review of safety, tolerability, and PK data from Parts A (SAD) and B (CYP3A4 Inhibition). Part D may be conducted in parallel with Part C.

Part D is optional and will assess the PK of single oral doses of LY3154885 in approximately 9 healthy subjects when administered as a capsule (Period 1), as a tablet (Period 2), and as a tablet with a high-fat diet (Period 3). The dose for Part D will not exceed the highest dose tested in Part A (SAD) that was deemed safe and well tolerated.

In Periods 1 and 2, subjects will be admitted to the CRU the afternoon of Day -2 for set up of baseline ABPM (see Section 9.4.4); admission for Period 3 will be on Day -1. In Period 1, subjects will undergo an overnight fast (see Section 6.3.1) before receiving a single oral dose of

LY3154885 (capsule formulation) on Day 1. Subjects will remain inpatient for at least 48 hours after dosing, after which they may be discharged at the discretion of the investigator. Subjects will be re-admitted to the CRU on Day 6 and will undergo an overnight fast before receiving a subsequent single oral dose of LY3154885 on Day 8 with the same formulation. Subjects will be discharged on Day 10, at least 48 hours after dosing. Re-admission to the CRU will be on Day 13, and following an overnight fast, subjects will receive a single oral dose of LY3154885 on Day 14 with the same formulation. Final discharge from the CRU will occur on Day 16. Pharmacokinetic sampling will be conducted as detailed in the Schedule of Activities (Section 2).

Period 2 will be conducted as described for Period 1; however, LY3154885 will be administered as a tablet formulation.

Period 3 will be conducted as described for Period 1; however, subjects will receive a single oral dose of LY3154885 (tablet formulation) after administration of a high-fat diet (see Section 6.3.1).

The follow-up visit will occur approximately 7 days after final discharge.

Figure HUAA.5.4 illustrates the study design for Part D.

	Period 1		Period 2		Period 3	
LY3154885 n=9	LY3154885 capsule (Days 1, 8 and 14)	≥7 day washout	LY3154885 tablet (Days 1, 8 and 14)	≥7 day washout	LY3154885 tablet after high fat meal (Days 1, 8 and 14)	≥7 day washout

Intensive PK sampling on Days 1, 8, and 14

Abbreviation: n = number of subjects; PK = pharmacokinetic.

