8.2. Discontinuation from the Study

Subjects will be discontinued in the following circumstances:

- Enrollment in any other clinical study involving an investigational product or enrollment in any other type of medical research judged not to be scientifically or medically compatible with this study

- Participation in the study needs to be stopped for medical, safety, regulatory, or other reasons consistent with applicable laws, regulations, and good clinical practice (GCP)
- Investigator Decision
 - the investigator decides that the subject should be discontinued from the study
 - if the subject, for any reason, requires treatment with another therapeutic agent that has been demonstrated to be effective for treatment of the study indication, discontinuation from the study occurs prior to introduction of the new agent
- Subject Decision
 - the subject requests to be withdrawn from the study
- If any of the potentially clinically significant vital sign criteria (Table HUAA.8.1) are met at 3 **consecutive scheduled** time points using in-clinic vital sign monitoring on Day 1 and following study drug dosing, the subject should be discontinued from the study drug. The relative value of the potentially clinically significant vital sign criteria is calculated by comparing the mean of the 3 supine BP and PR measurements at Time 0 on that day.

Table HUAA.8.1. Potentially Clinically Significant Vital Sign Criteria

	Low^a	High^a
Systolic BP (mm Hg)	≤90 AND ≥20 decrease	≥180 AND ≥20 increase
Diastolic BP (mm Hg)	≤50 AND ≥15 decrease	≥105 AND ≥15 increase
Pulse Rate (bpm)	≤50 AND ≥15 decrease	≥120 AND ≥15 increase

Abbreviations: BP = blood pressure, bpm = beats per minute, mm Hg = millimeters of mercury

^a Both conditions on absolute AND relative values are required for the measures to meet the criteria for potentially clinically significant (for example BP ≥180 AND ≥20 increase are both required for systolic blood pressure to meet the criteria for potentially clinically significant)

- For vital sign measurements that meet the criteria for potentially clinically significant vital signs (Table HUAA.8.1), action will be left to the discretion of the investigator and may include discontinuation of study drug or subject. Prior to subject being discontinued from the study, the investigator should consult with the Lilly clinical pharmacologist (CP) or designee.

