9.5.6 Ambulatory Blood Pressure Monitoring

Ambulatory blood pressure monitoring (ABPM) will be performed in all parts of the study. A 24 hours baseline (off study drug) will be measure in all subjects and at least a 2 hour measure prior to dose will be also be measured on selected dosing days. The ABPM device will record ambulatory BP and PR every 30 minutes during awake hours (e. g. 0700 hours to 2200 hours) and every 60 minutes throughout the night (e.g. 2200 hours to 0700 hours).

The primary parameters for the ABPM data will be peak hourly mean values of systolic blood pressure (SBP), diastolic blood pressure (DBP), and mean arterial pressure (MAP), and nadir hourly mean values for PR. These data will be listed and summarized by part and treatment.

Mean hourly SBP, DBP, MAP, and PR values will be calculated, summarized by part and treatment, and plotted, together with changes from baseline. Baseline value will be defined as the mean value during the 2 hours prior to the planned dosing time.

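### Vital-sign change is defined only from Day 1 predose; the later single doses in Part D (Days 8 and 14) and Part B (Day 14) also need a same-day change

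*SAP*

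**What the plan says.** SAP 9.5.4 summarizes vital signs by part, treatment and timepoint, with changes from baseline, "where baseline is defined as the Day 1 predose assessment". It makes no exception for any part, and no other SAP section changes this.

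Two parts give further single doses after Day 1:

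- **Part B (Protocol 5.1.2).** After the Day 1 dose, itraconazole is given "twice daily on Day 8 [dose separated by 12 hours], then once daily on Days 9 through 17", with subjects "receiving a single oral dose of LY3154885 or placebo on Day 14, approximately 1 hour after the dose of itraconazole".
- **Part D (Protocol 5.1.4).** Within each period, the Day 1 dose is followed by subjects "receiving a subsequent single oral dose of LY3154885 on Day 8 with the same formulation", and later "subjects will receive a single oral dose of LY3154885 on Day 14 with the same formulation".

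The Schedule of Activities (Protocol Section 2) includes predose vital signs for each of these doses. For Part B, its footnote a says: "Predose time points refer to dosing before itraconazole and LY3154885".

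Two other places use a same-day reference. SAP 9.5.6, on ambulatory monitoring, says: "Baseline value will be defined as the mean value during the 2 hours prior to the planned dosing time". Protocol 8.2 judges relative vital-sign change against "measurements at Time 0 on that day".

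**The concern.** A change score is meant to show what happened after the dose. In Part A, each dose falls on Day 1 of its own period, so on the natural reading a Day 1 baseline is also a same-day baseline. That no longer holds for the later doses in Parts B and D. There the score compares a reading after the dose with one taken one to two weeks earlier, although a reading from the same morning exists.

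In Part D the extra component is between-day drift. There is no placebo group from which to judge it, and Period 3 has no ambulatory monitoring as a second source. In Part B, six days of itraconazole also lie between the baseline and the dose. Safety of LY3154885 with itraconazole is a secondary objective, and Protocol 3.2 names cardiovascular effects among the nonclinical findings, so blood pressure and pulse profiles will be read closely. The same dose would also have a vital-sign profile and an ambulatory profile with different reference points.

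**Working it through.** The plan states no figure on this point, so there is none to reproduce. The check has four steps.

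**1. Age of the baseline**
- Part B: Day 14 − Day 1 = 13 days, with itraconazole on Days 8 to 13 (6 days).
- Part D: 8 − 1 = 7 days and 14 − 1 = 13 days. This takes Day 1 as that of the same period. The SAP does not say so, and if Period 1 were meant the gap would be longer in Periods 2 and 3.

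**2. Is the later predose reading a usable baseline?**
Protocol 3.2 projects a half-life of about 12 hours. The fraction remaining is 0.5^(hours/12).
- After 7 days (14 half-lives): 0.006%.
- After 6 days (Part D Day 8 to Day 14, 12 half-lives): 0.02%.

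On that projection the later predose readings are essentially free of LY3154885. (Protocol 5.4 gives a washout of at least 7 days for Part D. The 6-day gap needs reconciling with it, but does not affect this point.)

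In the extracted Part B schedule, the predose to 12-hour vital signs for the second dose appear beside Day 13. With the dose on Day 14 and the 24-hour reading on Day 15, I take them as Day 14.

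**3. What each change score contains at 2 to 12 hours**
Let L be the LY3154885 effect, I the itraconazole effect accumulated by the Day 14 predose reading, A the acute effect of that morning's itraconazole dose, d the drift shared by subjects since Day 1, and w the time-of-day effect.

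| | From Day 1 predose | From same-day predose | Difference |
|---|---|---|---|
| Part B Day 14 | L + A + w + I + d | L + A + w | I + d |
| Part D Days 8, 14 | L + w + d | L + w | d |

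In Part D Period 3 a meal effect is added to both scores. As an assumed illustration, take I from 0 to 5 and d from −5 to +5 mm Hg. The difference is then −5 to +10 mm Hg in Part B and −5 to +5 mm Hg in Part D.

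**4. Spread of the change score**
Drift that differs between subjects adds noise, not bias. Assume a systolic within-day SD of 5 mm Hg and a between-day SD of 4 to 8 mm Hg.
- From Day 1: √(2 × (25 + 16)) = 9.1, to √(2 × (25 + 64)) = 13.3.
- From the same day: √(2 × 25) = 7.1.
- Standard error of a mean change in 9 Part D subjects (divide by 3): 3.0 to 4.4, against 2.4 mm Hg.

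**Timepoints that benefit.** In Part B the readings after the Day 14 dose are at 2, 4, 8, 12, 24, 36, 48, 60, 72 and 96 hours, and 4 of these 10 fall on the dosing day. In Part D it is 4 of 6 (2, 4, 8 and 12, then 24 and 48 hours). On later days the between-day term returns, and in Part B further itraconazole doses enter.

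**The case against.** The strongest reply is that this is a choice of display and not an error, and much of it stands.

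- **Day 1 suits part of the Part B objective.** Change from a drug-free reading is the total change on the combination, a legitimate safety measure. A reader might infer that the Part B analysis is wrong. The documents do not support that, and the Day 1 change should stay.
- **Part B has more than its placebo group to work with.** A reader might infer that only the 3 placebo subjects can show the itraconazole effect. In fact all of the roughly 12 subjects take itraconazole before the Day 14 dose. SAP 6 lists itraconazole alone as its own treatment, and vital signs are scheduled on Days 8 and 9 and before the Day 14 dose.
- **Same-day information is partly visible already.** SAP 9.5.4 also summarizes and lists the values themselves. With the same subjects at both times, the mean same-day change is the difference between two displayed means. Its spread is not displayed.
- **The same-day references elsewhere mitigate the problem.** Ambulatory monitoring covers the Part B Day 14 dose and Part D Periods 1 and 2, and the subject-level criteria in Protocol 8.2 do not depend on SAP 9.5.4. Part D Period 3 remains uncovered.
- **No inference is at stake.** SAP 9.5.12 plans none for safety. The SDs above are assumptions.
- **The same-day change does not isolate LY3154885.** In Part B the acute effect of the Day 14 itraconazole dose remains.

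What remains is that the SAP defines no same-day vital-sign change for these doses. In Part D nothing in the design removes drift from the change it does define.

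**Conclusion.** The point holds as a low-cost improvement of minor severity. It is clearest for Part D Days 8 and 14, where the defined change carries 7 or 13 days of drift with no placebo. For Part B Day 14 the Day 1 change answers one valid question, and a same-day change would answer another: what followed the LY3154885 dose, given the itraconazole already on board.

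Under the assumed SDs, a dosing-day change from Day 1 is 28% to 89% more variable (9.06/7.07 = 1.28; 13.34/7.07 = 1.89). A reader might take that as a loss of precision in a planned comparison of LY3154885 with placebo. It is not, because the SAP plans no such vital-sign contrast. Nor does the itraconazole issue extend to Part D, which uses no itraconazole. The benefit is limited to the 2 to 12 hour readings, and Part C is unaffected. The conclusion that these predose readings are nearly free of LY3154885 rests on the projected half-life.

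**What to change.** Amend SAP 9.5.4 as follows:

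- **Part D, Days 8 and 14:** baseline is that day's predose reading in the same period. State that Day 1 means Day 1 of the period.
- **Part B, Day 14:** present two changes side by side. One is from the Day 14 predose reading, taken before itraconazole. The other is from Day 1 predose, labelled as total change on the combination. Note under the table that the first still contains the acute effect of that morning's itraconazole dose.
- **Part C:** keep Day 1 predose.

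The cost is a few lines of SAP text, the matching edits to the table and figure shells, and one extra column for Part B Day 14. The readings are already scheduled, so no new assessment or data collection is needed.

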9.5.5 ECG

The ECG data will be obtained directly from the 12-lead ECG traces. These data include the PR, QT, QRS duration and heart rate. In addition, QTcF (the QT interval corrected using Fridericia's formula) will be calculated as follows:

$$QTcF = \frac{QT}{\sqrt[3]{\frac{60}{HR}}}$$

The ECG data will be summarized by part, treatment and timepoint, together with changes from baseline, where baseline is defined as the mean of the triplicate assessment. Figures of mean ECG data and mean changes from baseline will be presented by treatment. The frequency of subjects with a maximum increase from baseline in QTcF interval will be summarized for each treatment according to the following categories: >30 ms and >60 ms. In addition, the frequency of subjects with QTcF postdose values, according to the following categories: >450 ms, >480 ms and >500 ms, will be summarized by treatment.

9.5.5.1 Electrocardiogram analysis (Part A)

The relationship between the time-matched LY3154885 concentrations and changes from baseline and time-matched placebo in QTcF interval will be explored graphically using a scatter plot. A regression analysis using a linear mixed-effects model will be performed. A plasma LY3154885 concentration-QT analysis will be performed to assess the changes from baseline (Day 1 predose) and time-matched mean placebo in the QTcF interval relative to plasma LY3154885 concentrations across all dose levels. The change from baseline adjustment will be based on individual subject's Day 1 predose value, and an additional placebo adjustment will be based on individual subject's time-matched placebo values. The analysis will be performed by plotting double delta QTcF against LY3154885 concentrations, including all post dosing timepoints. A linear mixed-effects model will be performed on the double delta QTcF values and will include LY3154885 concentration as a covariate. The estimated regression line and associated 90% confidence interval (CI) will be fitted on the plot and the p-value for the slope reported. Estimated delta QTcF and 90% CI at the geometric mean C_{max} (estimated from the highest given dose in the study) will also be presented.

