	Screening	Periods 1, 2, and 3					ED	Follow-up	Comments
Procedure	-28 to -3 days prior to dosing in Period 1	Day -2	Day -1	Day 1	Day 2	Day 3		At least 7 days after final dose	
Informed consent	X								
Admission to CRU		X (Period 1)	X (Periods 2&3)						
Discharge from CRU						X			
Medical history	X								
AE/medication review			X	X	X	X	X		
Height/weight	X						X	X	Height at screening only.
Neurological exam (hours)	X			Predose, 4, 8	24	48	X	X	
LY3154885/Placebo administration (hours)				0					
Vital signs (BP, PR [supine], temperature) (hours)	X		X	Predose, 2, 4, 8, 12	24, 36	48	X	X	Time points may be added for each study period, if clinically indicated. On Day 1, temperature will be measured at predose only.
ABPM			X	X	X				The ABPM on Day -1 is a 24-hour collection in Period 1 only (baseline measurement). See Section 9.4.4.
Clinical laboratory tests	X	X		Predose		X	X	X	See Appendix 2, Clinical Laboratory Tests, for details. PI must review the result of Day-2 results prior to Day 1 dose in Period 1 only.
Pregnancy test	X	X					X	X	Serum test at screening and admission of Period 1 only; urine test at all other time points.
PE/MA	X			Predose			X	X	Full PE/MA at screening and prior to final discharge from the study. Symptom-directed PE/MA at all other time points and as deemed necessary by the investigator.

continued

Study Schedule Protocol J1Z-MC-HUAA (Part A: Single-Ascending Dose – 3 Study Periods) (concluded)

	Screening	Periods 1, 2, and 3					ED	Follow-up	Comments
Procedure	-28 to -3 days prior to Period 1	Day -2	Day -1	Day 1	Day 2	Day 3		At least 7 days after final dose	
Single safety 12-lead ECG (hours)	X			Predose, 2, 4	24	48	X	X	
PK sampling (hours)				Predose, 0.5, 1, 2, 3, 4, 5, 6, 8, 12	24, 36	48			Sampling times are relative to the time of study treatment administration (0 hour).
Stored non-PGx plasma sample (hours)				Predose, 8	24				Stored sample for biomarker research. Sampling times are relative to the time of study treatment administration (0 hour).
PGx sample			X						Single sample for pharmacogenetic analysis taken prior to/on Day 1 of Period 1.
Urine collection (hours)				0-12, 12-24	24-36				Urine collection time starts from actual dosing time on Day 1 and finishes within \pm 30 minutes of the 36-hour time point.
Serum creatinine				Predose					To be collected at predose and sent to central laboratory.

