9.4.2. Vital Signs

For each subject, vital sign measurements should be conducted according to the Schedule of Activities (Section 2). Vital signs will comprise BP, PR, and body temperature.

For supine measurements of BP and PR, subjects should be in the supine position for at least 5 minutes before the procedure.

Unscheduled orthostatic vital signs should be assessed, if possible, during any AE of dizziness or posture-induced symptoms. Additional vital signs may be measured during each study period if warranted.

For orthostatic measurements of BP and PR, subjects should be supine for at least 5 minutes and stand for at least 2 minutes for supine and standing measurements, respectively. If the subject feels unable to stand, supine vital signs only will be recorded.

9.4.3. *Electrocardiograms*

For each subject, ECGs should be collected according to the Schedule of Activities (Section 2).

Any clinically significant findings from ECGs that result in a diagnosis and that occur after the subject receives the first dose of the investigational product should be reported to Lilly or its designee as an AE via the CRF.

At screening, early discontinuation, and follow-up, a single ECG will be obtained and does not need to be transmitted to the ECG vendor. The screening ECG will be interpreted by the investigator or qualified designee at the site to determine whether the subject meets entry criteria. In Parts A, B and D, single ECGs will be collected at all time points.

In Part C, at all time points other than screening, early discontinuation, and follow-up, ECGs will be collected in triplicate.

Electrocardiograms should preferably be recorded before collecting any blood samples. Subjects must be supine for approximately 5 minutes before ECG collection and remain supine but awake during ECG collection. Consecutive replicate ECGs will be obtained at approximately 1-minute intervals. Electrocardiograms may be obtained at additional times, when deemed clinically necessary. Collection of more ECG replicates than expected at a particular time point will be permitted to ensure high-quality records.

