9.5.5.2 Electrocardiogram analysis (Part C)

The same analysis to Part A will be performed in Part C, but the change from baseline adjustment will be based on individual subject's Day 1 predose value, and an additional placebo adjustment will be based on mean time-matched placebo values.

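### The Part A concentration-QTc model subtracts a single predose ECG at full weight and does not adjust for it, so the QTcF estimate at Cmax is less precise than the collected data allow

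*SAP*

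**What the plan says.** SAP 9.5.5.1 builds the Part A response by two subtractions. First: "The change from baseline adjustment will be based on individual subject's Day 1 predose value". Second: "an additional placebo adjustment will be based on individual subject's time-matched placebo values". The model is then described as follows: "A linear mixed-effects model will be performed on the double delta QTcF values and will include LY3154885 concentration as a covariate". No predose, time or treatment term is named, and the random effects are not stated. The outputs are a slope p-value and an estimate with 90% CI at the geometric mean Cmax of the highest dose.

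Three other statements bear on this.

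- Replicates: Protocol 9.4.3 states "In Parts A, B and D, single ECGs will be collected at all time points". The Part A schedule places these ECGs at predose, 2, 4, 24 and 48 h in each period.
- Baseline: SAP 9.5.5 says "where baseline is defined as the mean of the triplicate assessment". SAP section 3 shows that the SAP was written from amendment (a). Protocol Appendix 6 shows that amendment (b) reduced Part A to single ECGs.
- Placebo: the same paragraph of SAP 9.5.5.1 also refers to "time-matched mean placebo in the QTcF interval relative to plasma LY3154885 concentrations across all dose levels", which does not agree with an individual correction.

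**The concern.** Subtracting a baseline gives it a fixed weight of one. That weight is too high when the baseline is measured with error, because the error goes into the response unchanged. In Part A the baseline is one ECG, and its error is common to all four postdose values of the period. If each subject's own placebo period is used, the placebo-day predose error also enters both active periods. A predose covariate lets the data choose the weight.

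At stake is the width of the 90% CI at Cmax, which is the main quantitative QT result from Part A. The readings needed to tighten it are already collected.

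**Working it through.** The documents give no precision target, power or SD for QTcF, so there is no planned figure to reproduce.

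**Inputs from the documents.** 24 subjects in two cohorts; two active periods and one placebo period each; doses 15, 45, 100, 200, 400 and 500 mg; single ECGs at predose, 2, 4, 24 and 48 h; projected half-life about 12 h; washout at least 7 days; 90% CI.

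**Assumptions.** Single-ECG SD s, day-to-day SD t, absorption rate 1/h, exposure variability about 30%, true effect 5 ms at the 500 mg peak, individual placebo correction, random subject intercept (the SAP names no random effects).

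**Step 1: variance of one double-delta value.** Let D be the active-minus-placebo postdose difference and D0 the same difference at predose.

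- Var(D) = Var(D0) = 2s² + 2t², and Cov(D, D0) = 2t².
- Planned value D − D0: variance 2(2s² + 2t²) − 2(2t²) = 4s².
- Adjusted for D0: variance 2s² + 2t² − (2t²)²/(2s² + 2t²).
- Planned minus adjusted = 2s⁴/(s² + t²), which is always positive.

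The predose/postdose correlation within a subject is t²/(s² + t²).

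| t / s (ms) | Correlation | Planned variance | Adjusted variance | SD, planned to adjusted |
|---|---|---|---|---|
| 3 / 8 | 9/73 = 0.12 | 256 | 146 − 324/146 = 143.8 | 16.0 to 12.0 |
| 6 / 6 | 36/72 = 0.50 | 144 | 144 − 5184/144 = 108 | 12.0 to 10.4 |
| 8 / 4 | 64/80 = 0.80 | 64 | 160 − 16384/160 = 57.6 | 8.0 to 7.6 |

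**Step 2: SD of the estimate at the 500 mg Cmax, by simulation.** The half-width is 1.645 × SD.

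| t / s | Planned SD | Adjusted SD, predicted at D0 = 0 | Fall | 90% half-width |
|---|---|---|---|---|
| 3 / 8 | 3.24 | 2.30 | 1 − 2.30/3.24 = 29% | 5.3 to 3.8 |
| 6 / 6 | 2.59 | 2.15 | 1 − 2.15/2.59 = 17% | 4.3 to 3.5 |
| 8 / 4 | 1.73 | 1.67 | 1 − 1.67/1.73 = 3% | 2.8 to 2.7 |

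A second set of 1,000 trials per setting gave 3.37 to 2.32, 2.65 to 2.16 and 1.67 to 1.55 ms, falls of 31%, 18% and 7%. Over s from 5 to 12 and t from 0 to 5, the adjusted SD was 0.62 to 0.84 of the planned one. At t = 10 the ratio was 0.88 (s = 8) and 0.95 (s = 5). With a subject-by-period intercept and s = 8, it was 0.63, 0.72, 0.80 and 0.91 for t = 0, 3, 5 and 10. No setting showed a loss, and the planned and adjusted estimates were both unbiased (means about 5 against a true 5).

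**Step 3: where to evaluate the prediction.** Both predose readings precede dosing in randomized periods. The washout of at least 168 h is 168/12 = 14 projected half-lives, so D0 has expectation zero. Predicting at the sample mean of D0 puts its chance imbalance back into the estimate, while the model standard error ignores it. The SD is then 2.95 ms at 3/8 and 2.34 ms at 6/6, with 90% CI coverage of 80% and 85%.

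**Step 4: effect of moving to single ECGs.** With s = 8 and the planned model, a triplicate predose would have given an SD of 2.61 ms, against 3.39 ms with a single predose in the same runs. The loss is therefore larger under amendment (b) than under the design for which the SAP was written.

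**The case against.** The strongest reply is that this analysis is supportive. The primary endpoint is TEAE incidence, the study is not powered for hypothesis tests, SAP 9.5.12 plans no inferential safety analysis, and every SD used above is assumed. That stands, and it limits the weight of the point. It does not change the direction, which follows from the algebra under individual placebo correction.

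It is also fair that the single predose ECG was not the SAP's choice. The SAP assumed triplicates, and the protocol changed afterwards. The conflict over mean or individual placebo stands too: the figures above hold for the individual reading only.

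A reader might infer three stronger points that are not supported.

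- **That Part C needs the same change**, because SAP 9.5.5.2 says "The same analysis to Part A will be performed in Part C". Part C has replicate predose ECGs, a random subject intercept would already absorb a subject-constant baseline error, and the mean placebo value that is subtracted stays unadjusted. Simulated SDs without and with the covariate were 4.52 and 4.53, 2.71 and 2.72, and 4.31 and 4.26 ms: no useful gain.
- **That leaving out the covariate makes the slope test anti-conservative.** With no true effect and a nominal 10% level, the planned model with a subject-only intercept rejected 15 to 17% of the time. A subject-by-period intercept with no covariate brought this to 11 to 12%. The inflation comes mainly from the random-effect structure, which the SAP leaves open.
- **That the planned estimate is biased.** It is not; it is only noisier.

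**Conclusion.** The point holds for Part A as a loss of precision. Under the individual-placebo reading the planned response has variance 4s², and adjustment for the predose difference always reduces it. The SD of the Cmax estimate falls by about 30% if single-ECG noise dominates, about 17% if day-to-day and ECG noise are equal, and about 3% (7% in the second set of runs) if day-to-day variation dominates. These sizes rest on assumed SDs, an assumed PK shape and an assumed random subject intercept. The gain under a mean-placebo correction was not quantified. The benefit depends on predicting at a predose difference of zero. The TEAE endpoint is not affected.

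**What to change.** Replace the model sentence in SAP 9.5.5.1, for Part A only, with wording such as:

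> The model will include LY3154885 concentration and the active-day minus placebo-day predose QTcF difference (uncentred) as fixed effects, with random intercepts for subject and period within subject. The estimate and 90% CI at the geometric mean Cmax will be computed at a predose difference of zero.

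Do not compute the prediction at the sample mean of the predose difference.

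In the same edit:

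- Settle whether the Part A placebo correction uses the individual or the mean value. The covariate above fits the individual correction. If the mean is kept, the covariate must be redefined and the gain worked out again.
- Replace the triplicate baseline in SAP 9.5.5 for Part A, where the protocol now specifies single ECGs.

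Leave the covariates in SAP 9.5.5.2 (Part C) as they are.

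The cost is one model term and one degree of freedom, with no new data. SAP 9.5.5 has to be reopened in any case to match amendment (b).
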